## 10.3 Duration of Subject Participation

The expected duration for each subject's participation in the study is up to 32 weeks, including a 24-week treatment period, and an 8-week follow-up period (12 weeks after the last study drug injection at Week 20).

### 10.3.1 Early Termination Visit

If a subject meets the criteria for relapse at any point during the treatment period, the subject will be eligible to re-enter the LTE study (see [Figure 2](#)). Subjects who exit the study before Week 24 should complete an ET visit. For subjects re-entering the LTE study, a minimum of 3 weeks is required between doses of study drug. Subjects who prematurely discontinue study drug for reasons other than relapse will be encouraged to complete the scheduled study visits. These subjects will only be eligible for re-enrollment in the LTE study if they continue with study visits through Week 24.

A follow-up visit will be conducted 8 weeks after completing the treatment period and/or 12 weeks ( $\pm 7$  days) after the last study drug injection for all subjects who will **not** continue nemolizumab treatment in the LTE study. Twelve weeks corresponds to approximately 5 half-lives of nemolizumab when administered subcutaneously Q4W at the doses used in this study.

### 10.3.2 Unscheduled Visit

The subject should be reminded to adhere to the study schedule. Unscheduled visits are defined as visits to repeat testing for abnormal laboratory results, for follow-up of AEs, or to conduct efficacy assessments for subjects requiring rescue medication between regularly scheduled study visits. Visits occurring outside of the visit window are not considered unscheduled visits.

Assessments to be conducted at the unscheduled visit will depend on the reason for the visit: any of the procedures/assessments listed in [Table 7](#) may be conducted, but not all are required. Blood sample collection for POE and ADA analyses are required during unscheduled visits that are conducted for safety reasons when safety labs are collected for the management/monitoring of an AE. When a series of unscheduled visits is needed for the monitoring of the same AE, the POE and ADA collection is not required if already done at the first unscheduled visit of the series. Additional collection of samples for POE and ADA analysis should be performed per Investigator's judgment.

## 11 EFFICACY ASSESSMENTS

### 11.1 Investigator Global Assessment

The IGA is a 5-point scale used by the Investigator or trained designee to evaluate the global severity of PN. The Investigator will review the subject's skin and give a score of 0 (clear), 1 (almost clear), 2 (mild), 3 (moderate), or 4 (severe). Treatment response/success is defined as 0 (clear) or 1 (almost clear) (see [Appendix 3](#)).

The same evaluator should perform all assessments for the same subject in order to reduce intra-subject variability.

### 11.2 Numeric Rating Scales

#### 11.2.1 Peak Pruritus Numeric Rating Scales

An NRS relating to maximum intensity itch/pruritus (PP NRS) will be completed by the subject (see [Appendix 4](#)). The NRS will ask for a unit score on an 11-point scale (0 to 10) where 0 is "no itch" and 10 is the "worst itch imaginable". CCI

#### 11.2.2 Sleep Disturbance Numeric Rating Scale

An NRS relating to sleep disturbance (SD NRS) will be completed by the subject to report the degree of their sleep loss related to PN (see [Appendix 5](#)). The SD NRS will ask for a unit score on an 11-point scale (0 to 10). The question asked will be: "On a scale of 0 to 10, with 0 being "no sleep loss related to the symptoms of my skin disease (prurigo nodularis)" and 10 being CCI

### 11.3 Quality of Life Questionnaires

#### 11.3.1 Dermatology Life Quality Index

The DLQI is a validated 10-item questionnaire covering domains including symptoms/feelings, daily activities, leisure, work/school, personal relationships, and treatment (see [Appendix 6](#)).

The subject will rate each question ranging from 0 (not at all) to 3 (very much). A higher total score indicates a poorer QoL.

## 12 SAFETY ASSESSMENTS

### 12.1 Vital Signs

Vital signs will be evaluated at all visits as indicated in the Schedule of Assessments ([Table 7](#)). Vital signs will include pulse rate, systolic and diastolic blood pressure (after the subject has been sitting for at least 5 minutes), and body temperature. All abnormal values at the baseline visit identified as clinically significant by the Investigator will be recorded in the medical history form. Any clinically significant changes from the baseline visit (and onwards) will be recorded as an AE.

### 12.2 Height and Weight

Height and weight will be measured according to the Schedule of Assessments ([Table 7](#)).

### 12.3 Physical Examination

A complete physical examination should be performed according to the Schedule of Assessments ([Table 7](#)) at designated visits. A complete physical examination will include assessments of the head, ears, eyes, nose, throat, neck (including thyroid), skin/integumentary system, cardiovascular system, respiratory system (for additional respiratory assessments, see [Section 12.6](#)), gastrointestinal system, musculoskeletal system, lymph nodes, nervous system, and extremities.

A symptom-directed physical examination should be performed at all other visits according to the Schedule of Assessments ([Table 7](#)).

The Investigator should assess all abnormal findings for clinical significance. All clinically significant abnormal findings at the baseline visit will be recorded in the medical history form. Any clinically significant changes from the baseline visit will be recorded as an AE.

### 12.4 12-lead Electrocardiogram

A 12-lead, resting ECG will be performed and read centrally according to visits indicated in the Schedule of Assessments ([Table 7](#)). The 12-lead ECGs for each subject should be obtained using the electrocardiograph machine provided for the study. The 12-lead ECGs will be performed in the supine position and before any scheduled vital sign measurements and blood draws. Subjects should be monitored for potentially clinically significant ECG results (refer to the current version of the central laboratory manual). Tests with abnormal results at the baseline visit should be recorded in the medical history form. Results that are deemed clinically significant should be repeated to ensure reproducibility of the abnormality. Any abnormalities considered by the Investigator to be clinically significant after the baseline visit are to be recorded as AEs and discussed with the Medical Monitor, as needed.

## 12.5 Clinical Laboratory Evaluation

Laboratory assessment samples are to be obtained at designated visits as detailed in the Schedule of Assessments ([Table 7](#)).

The hematology laboratory analyses, clinical chemistry laboratory analyses, and urinalyses will be performed at a central laboratory. Reference ranges will be supplied by the central laboratory and used by the Investigator to assess the laboratory data for clinical significance and pathological changes.

The Investigator or medically qualified Sub-investigator must review and evaluate laboratory values for each subject in a timely manner. Study centers should refer to the current version of the laboratory manual for laboratory values outside of normal limits. For each out-of-range laboratory result, the Investigator or designee will evaluate whether he/she considers it to be clinically significant, defined as meeting at least 1 of the following conditions:

- The abnormality suggests a disease and/or organ toxicity, or
- The abnormality is of a degree that requires additional active management, e.g., discontinuation of the drug, close observation, more frequent follow-up assessments, or further diagnostic investigation.

If the Investigator observes a clinically significant laboratory result, the test will be repeated as soon as possible, and the subject will be monitored until the value returns to normal and/or an adequate explanation for the abnormality is found.

Investigators will also be allowed to repeat specific laboratory test(s) or procedure(s) where the Investigator suspects an inaccuracy or false result and that which may impact the safety of the subject or the interpretation of the trial results. This should occur only after discussion with Medical Monitor.

All clinically significant out-of-range laboratory values at the baseline visit will be recorded (report a diagnosis rather than the laboratory value whenever possible) in the medical history form. All clinically significant out-of-range laboratory values after the baseline visit are to be reported as an AE if this abnormality was not present at the baseline visit, or is assessed as having worsened since the baseline visit (i.e., changed significantly from the baseline visit). Whenever possible, the Investigator should provide a diagnosis of an AE when reporting the abnormal laboratory value. See Section [12.7](#) for details.

Subjects should be reminded to be well hydrated before all visits for phlebotomy purposes. Subjects should fast for at least 8 hours before the visits when blood chemistry testing is planned. Laboratory testing conducted in a non-fasting state will not be a protocol deviation.

Total blood volumes to be drawn at each visit are provided in the clinical laboratory manual and in [Appendix 8](#). Additional samples may be required if medically indicated (e.g., at unscheduled visits for safety reasons, when an abnormal laboratory value is observed and requires a re-test).

### **12.5.1 Hematology**

The hematology tests include: hemoglobin, hematocrit, white blood cell count (with differential including eosinophils), red blood cell count, platelet count, and mean cell volume.

### **12.5.2 Clinical Chemistry**

The clinical chemistry tests include: creatinine, aspartate aminotransferase (AST), alanine aminotransferase (ALT), gamma glutamyl transferase, alkaline phosphatase, lactate dehydrogenase, total bilirubin, direct bilirubin, albumin, total protein, uric acid, sodium, potassium, calcium, chloride, glucose, urea, total cholesterol, triglycerides, low-density lipoprotein, high-density lipoprotein, creatine phosphokinase (CPK). CPK isoenzyme test will be performed only if CPK is elevated to  $>2.5 \times$  upper limit of normal (ULN). The Investigator should also contact the Medical Monitor in such situations.

For postmenopausal subjects (i.e., no menses for 1 year), the blood chemistry sample at the baseline visit will also be used to confirm postmenopausal status by a high FSH level in the postmenopausal range, unless previously confirmed as part of the lead-in study.

### **12.5.3 Urinalysis**

The urinalysis tests include: pH, glucose, ketones, blood, protein, leukocytes, nitrites, bilirubin, urobilinogen, and specific gravity.

### **12.5.4 Pregnancy Testing**

Urine pregnancy tests (UPTs) will be conducted for all women of childbearing potential beginning at baseline and continuing at subsequent visits according to the Schedule of Assessments ([Table 7](#)). Pregnancy test results must be available prior to the administration of the study drug.

UPTs with a sensitivity  $<25$  IU/L will be provided to the study centers for use in the trial.

UPTs will be performed at the study centers, and all other samples will be sent to central laboratory for analysis.

If the result of a UPT is positive, it must be confirmed with a serum pregnancy test, and no study drug should be administered pending the serum pregnancy test result. Subjects with a positive serum pregnancy test result during the trial must discontinue treatment and be withdrawn from the trial.

### **12.5.5 Follicle-stimulating Hormone**

The postmenopausal status (defined as no menses for 1 year) of a subject will be confirmed at the baseline visit, unless previously confirmed as part of the lead-in study. For these subjects, postmenopausal status will be confirmed with a FSH level in the postmenopausal range.

Blood chemistry sample at the baseline visit will also be used for an FSH test for the confirmation of postmenopausal status, if applicable.

## 12.5.6 Virology

Virology including hepatitis B surface antigen (HBsAg), hepatitis B core antibody (HBcAb), hepatitis C virus (HCV), human immunodeficiency virus 1, and human immunodeficiency virus 2 antibodies may be assessed at unscheduled visits for safety purposes based on Investigator judgment. Subjects with a positive HBcAb and a negative HBsAg will also be assessed for hepatitis B surface antibody. Subjects with positive HCV antibodies will have a confirmatory test for HCV (e.g., polymerase chain reaction).

## 12.5.7 Tuberculosis Testing

Subjects may be assessed for active or latent tuberculosis (TB) at unscheduled visits for safety purposes based on Investigator judgment. A subject who tests positive for latent TB (with a positive QuantiFERON-TB Gold test) should be referred to the subject's treating physician for appropriate follow-up.

## 12.6 Respiratory Assessments

At baseline, the Investigator should specifically question all subjects about any medical history or changes in their asthma and respiratory health (e.g., wheezing, coughing, allergies, and infections). Subjects with a history of asthma will be questioned about the seasonality of their asthma and known triggers, such as allergens. Newly-diagnosed asthma or worsening of asthma during the study will be reported as an AESI.

### 12.6.1 Asthma Control Test

Subjects with a medical history of asthma will take the ACT at all visits according to the Schedule of Assessments ([Table 7](#)) before questioning and physical examination by the Investigator. Subjects with a new (de novo) diagnosis of asthma will take the ACT at the visit the diagnosis was first confirmed and thereafter, at all subsequent study visits. Subjects with an ACT score  $\leq 19$  will be referred to the physician managing their asthma.

The ACT is an assessment to determine if a subject's asthma symptoms are well controlled. The ACT is designed for adults and adolescents 12 years or older, and is composed of 5 questions. For each question, the subject will choose the best answer out of 5 possible answers. The test provides a numerical score ranging from 5 to 25 to assess asthma control; a higher score indicates better asthma control while a score of 19 or less indicates the subject's asthma may not be under control. A copy of the ACT can be found in [Appendix 7](#).

### 12.6.2 Respiratory Examination

A respiratory examination will be required to be performed for all subjects at specified visits according to the Schedule of Assessments ([Table 7](#)). Only subjects reporting a medical history of asthma will require a respiratory examination at all visits. Subjects with a new (de novo) diagnosis

of asthma will require a respiratory examination at all scheduled visits after the diagnosis is first made according to the Schedule of Assessments ([Table 7](#)).

The ACT will also aid the Investigator's questioning of subjects with a medical history of asthma and should be completed before the clinical questioning. All subjects will be asked non-leading questions about any respiratory changes. The Investigator or designee will then perform a respiratory examination of all subjects at all visits.

Subjects with a medical history of asthma will be referred to the physician managing their asthma if unexpected worsening of asthma is observed or reported. Subjects without a medical history of asthma who experience respiratory changes (examination findings or newly-reported signs and/or symptoms suggestive of asthma) will be referred to a respiratory specialist.

### **12.6.3 Peak Expiratory Flow**

All subjects will undergo PEF testing at specified visits according to the Schedule of Assessments ([Table 7](#)). Only subjects reporting a medical history of asthma will undergo PEF testing at all visits.

Subjects with a new (de novo) diagnosis of asthma will undergo PEF testing at all scheduled visits after the diagnosis is first made according to the Schedule of Assessments ([Table 7](#)).

Peak expiratory flow testing during the clinical study will be performed under the supervision of qualified study personnel. Peak expiratory flow measurements should consist of 3 good efforts, with the best result documented. It is preferable that the PEF measurement be performed before noon or at the same time during each study visit whenever possible. Obtained PEF values will be compared to predicted values based on the subject's age, sex and height.

To avoid interference with PEF measurements, attempts should be made to withhold asthma medication on study visit days until after PEF testing is complete; to the extent it does not pose an undue risk to the subject.

Subjects with a medical history of asthma with a PEF <80% of the predicted value will be referred to the physician managing their asthma.

### **12.6.4 Respiratory Referrals**

Subjects with a medical history of asthma will be referred to the physician who manages their asthma when:

- PEF <80% of the predicted value
- ACT score  $\leq 19$  because an ACT score  $\leq 19$  conveys asthma that may not be adequately controlled
- Unexpected worsening of asthma is observed or reported at any time during the study

At any study visit, subjects without a medical history of asthma will be referred to an appropriate respiratory/asthma specialist physician whenever:

- Signs and/or symptoms suggestive of asthma are newly observed or reported
- Respiratory assessments (i.e., examination, PEF) suggest a decline in the subject's respiratory health

## 12.7 Adverse Events

### 12.7.1 Adverse Events

An AE is defined as any untoward medical occurrence in a clinical study subject administered a medicinal product which does not necessarily have a causal relationship with this treatment. An AE can therefore be any unfavorable and unintended sign (including an abnormal laboratory finding), symptom, or disease temporally associated with the use of a medicinal (investigational) product, whether or not it is related to the medicinal (investigational) product. This includes an exacerbation of pre-existing conditions or events, intercurrent illnesses, drug interaction, or the significant worsening of the indication under investigation that is not recorded elsewhere in the eCRF under specific efficacy assessments.

Note(s):

- Any new sign or symptom reported by the subject that appears after accidental or intentional overdose or misuse should be reported as an AE.
- Whenever possible, a diagnosis should be reported on the AE form, instead of signs, symptoms, or abnormal laboratory values.
- Pregnancy is not to be considered an AE; however, it must be monitored and reported as described in Section [12.7.7](#).
- Each worsening of a chronic disease from the baseline visit should be reported as a new AE.

The Investigator or designee will report all AEs that occur from the time the ICF is signed until the end of the study. The Sponsor/CRO should be informed if the Investigator becomes aware of any safety information that appears to be drug related, even after the subject has completed the clinical study.

At each post enrollment visit, the Investigator (or Sub-investigator) will question the subject about AEs using an open non-persuasive question to elicit reporting of AEs (for example, "Have you noticed any change in your health since the last visit?"). Directed questioning and examination will then be performed as appropriate.

Any AE occurring during the AE reporting period, whether it is related to the study drug or not, will be recorded immediately in the source document and described on the Adverse Event Form ("AE Form") along with the date of onset, severity, relationship to the study drug(s), and outcome, without omitting any requested and known information. Additional information will be requested under certain circumstances.

Adverse events assessed as related to the treatment or study procedure will be monitored until they have resolved or reached a stable condition. Other AEs will be monitored until the last visit if they have not resolved or reached a stable condition.

The Investigator will obtain and maintain in the subject's files all pertinent medical records, information and medical judgment from colleagues who assisted in the treatment and follow-up of the subject. If necessary, the Investigator will contact the subject's personal physician or hospital staff to obtain further details.

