## 7 INVESTIGATIONAL PLAN

### 7.1 Description of Overall Study Design and Plan

[figure not shown]
This is a Phase 3b multicenter, randomized, double-blind, placebo-controlled, parallel-group withdrawal study to evaluate the durability of response and safety of nemolizumab in adult subjects with PN who participated in the nemolizumab PN LTE study (RD.06.SPR.202699) and achieved a clinical response (i.e., IGA score of 0 or 1 and  $\geq 4$ -point improvement in weekly average of PP NRS score from baseline of the lead-in study) at Week 52 of the LTE study.

Subjects who agree to enroll in this study must do so at the time of completion of the Week 52 visit in the LTE study (RD.06.SPR.202699) to prevent any lapse in study treatment. After the Week 52 visit of the LTE study is complete, approximately 40 subjects who choose to enter this study will be randomized 1:1 to either continue the same dosing regimen received in the LTE study (i.e., 1 or 2 SC injections of study drug administered Q4W), or to discontinue nemolizumab and receive placebo.

Subjects' participation in the study will be up to approximately 32 weeks. The study consists of a 24-week treatment period and an 8-week follow-up period (12 weeks after their last study drug injection at Week 20).

Relapse is defined as an increase in (weekly average of the) PP NRS score  $\geq 4$  points from baseline or an increase in IGA score  $\geq 2$  from baseline at any point during the study. If a subject meets the criteria for relapse, then the subject may be considered for re-entry into the LTE study (RD.06.SPR.202699) (see [Figure 2](#)).

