### **8.3 Removal of Subjects from Therapy or Assessments**

Although the importance of completing the entire clinical study will be explained to the subjects, any subject is free to discontinue his/her participation in the study at any time and for whatever reason, specified or unspecified, and without any prejudice. No constraints are to be imposed on the subject, and when appropriate, a subject may be treated with other conventional therapy when clinically indicated. Investigators or the Sponsor can also withdraw subjects from the clinical study if deemed to be necessary.

Reasons for discontinuing study drug include:

- Subject request (i.e., consent withdrawal)
- Non-compliance with the study drug or study schedule
- Lost to follow-up
- Occurrence of AEs, including TEAE and laboratory abnormalities, not compatible with the continuation of subject participation in the study, in the Investigator's opinion, or unacceptable to the subject to continue, including but not limited to the following:
  - Serious immediate-type allergic manifestations including anaphylactic reaction
  - Serious worsening of asthma considered related to study drug administration
  - Diagnosis of a malignancy (except curatively treated in situ cervical carcinoma, squamous cell carcinoma [Bowen's disease], or basal cell carcinoma)

- Opportunistic infections such as but not limited to active tuberculosis (TB) and other infections whose nature or course suggest an immune-compromised or immune-suppressed status
- Any serious infection or any severe infection requiring treatment with parenteral antibiotics or oral antibiotics/antivirals/antifungals for >2 weeks considered related to study drug administration
- Confirmed or suspected COVID-19 infection (temporary discontinuation may be acceptable; for instructions on resuming study drug administration, see Section 8.3.2).
- Pregnancy (see Section 8.3.1)
- Use of non-permitted concurrent therapy (as specified in Section 9.6.3, unless discussed and agreed upon with the Investigator and Medical Monitor)
- Use of systemic rescue therapy (as specified in Section 9.6.2)
- Treatment failure (subjects who relapse may be eligible to re-enroll in the LTE study)
- Investigator request
- Sponsor request, including any of the above criteria

The reason(s) for withdrawal will be documented in the electronic case report form (eCRF). Subjects who have been enrolled and treated will not be replaced by another subject.

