### 9.6.2     Rescue Therapy

Rescue therapies are not permitted in this study. Subjects enrolled in this study have demonstrated a clinical response to nemolizumab; therefore, if a subject experiences relapse, they will be discontinued from this study and may be eligible to continue to receive nemolizumab by re-enrolling in the LTE study (see [Figure 2](#)).

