13.5. Physical Examination

Following body system assessments will be performed at Baseline/Day 1, Week 12, Week 24, Early Termination, and Week 32/Follow-up:

- Head, ears, eyes, nose, throat, neck (including thyroid),
- Skin/integumentary system (excluding PN),
- Cardiovascular system,
- Respiratory system,
- Gastrointestinal system,
- Musculoskeletal system,
- Lymph nodes,
- Nervous system, and
- Extremities.

The number and percentage of subjects with physical examination results by body system classified as 'Normal', 'Abnormal, NCS' or 'Abnormal, CS' will be summarized (Baseline and scheduled visits only).

Shift from Baseline of the physical examination category will also be summarized by body system.

This document is confidential.

By-subject listing will be provided for subjects who have at least one abnormal result from any body system or who missed the assessment due to any reason.

All physical examination results will be listed on the Safety population.

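### The plan does not settle whether a relapse already recorded as IGA or PP NRS is also an adverse event, so uneven site reporting could raise placebo TEAE rates

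*Protocol*

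**What the plan says.** **The carve-out.** The AE definition in Protocol 12.7.1 covers worsening of the studied disease only as "significant worsening of the indication under investigation that is not recorded elsewhere in the eCRF under specific efficacy assessments". Relapse (Protocol 7.1) is a PP NRS rise of at least 4 points or an IGA rise of at least 2 points. Both are efficacy assessments, so a relapse falls outside this wording.

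**The general rules.** A note in the same section says "Each worsening of a chronic disease from the baseline visit should be reported as a new AE". Protocol 12.3 says of physical examination findings: "Any clinically significant changes from the baseline visit will be recorded as an AE". The body systems it lists include "neck (including thyroid), skin/integumentary system, cardiovascular system", with no exception for PN lesions.

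**The SAP.** SAP 13.5 describes the same examination with the skin item as "Skin/integumentary system (excluding PN" and schedules it at early termination among other visits. Relapsing subjects should complete that visit (Protocol Table 7, note b).

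**Exit at relapse.** Under Protocol 9.6.2, "if a subject experiences relapse, they will be discontinued from this study". Protocol 8.3 lists treatment failure, which includes relapse, as a reason for stopping study drug separate from the occurrence of AEs.

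**The tables.** The TEAE definition and table list in SAP 13.1 have no rule that removes PN-worsening terms or reports them separately.

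**The concern.** PN is a chronic disease, and a relapse is a worsening from baseline that is often visible on the skin. A site that follows the note or 12.3 literally would file it as an AE. A site that follows the definition would not. Nothing tells sites which text prevails, and the open question about changes in health at each visit (12.7.1) invites a relapsing subject to report itch.

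The secondary objective is the safety of nemolizumab against placebo. In a randomized withdrawal design, relapse is the efficacy outcome and is expected mainly on placebo. Relapses filed as AEs would raise the placebo lines for any TEAE, severe TEAEs and the skin system organ class. They would also raise the exposure-adjusted rates, because a subject who exits early adds an event against little exposure time. In those aggregate lines, a real excess of other events on nemolizumab could be offset. Once sites have reported unevenly, the analyst cannot recover what a uniform rule would have produced.

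**Working it through.** **Texts side by side**

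- The definition in 12.7.1 addresses the indication directly. It excludes what the efficacy assessments already record, by implication.
- The note in 12.7.1 is a general rule on chronic disease. It does not name PN and has no exception for the indication.
- Protocol 12.3 is a general rule on clinically significant examination changes, as judged by the Investigator. Skin is included and PN is not excepted.
- SAP 13.5 covers the same examination with PN excepted.

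The first and fourth texts point one way. The second and third, read literally, point the other way.

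**Size**

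The plan has no figure to reproduce. It gives no relapse rate or background TEAE rate, and Protocol 14.1 states that no formal sample size calculation was done. All rates below are assumptions.

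Let b be the background TEAE proportion, equal in both arms, and r the relapse proportion, taken as independent of b. If every relapse is filed as an AE:

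- TEAE proportion = 1 - (1 - b)(1 - r)
- Excess on placebo = (1 - b)(r placebo - r nemolizumab)

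| b | r, placebo / nemolizumab | TEAE placebo | TEAE nemolizumab | Excess on placebo (points) |
|---|---|---|---|---|
| 30% | 20% / 5% | 44.0% | 33.5% | 10.5 |
| 30% | 40% / 10% | 58.0% | 37.0% | 21.0 |
| 30% | 60% / 15% | 72.0% | 40.5% | 31.5 |
| 30% | 70% / 20% | 79.0% | 44.0% | 35.0 |
| 40% | 60% / 15% | 76.0% | 49.0% | 27.0 |
| 50% | 20% / 5% | 60.0% | 52.5% | 7.5 |
| 50% | 40% / 10% | 70.0% | 55.0% | 15.0 |
| 50% | 60% / 15% | 80.0% | 57.5% | 22.5 |
| 50% | 70% / 20% | 85.0% | 60.0% | 25.0 |

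Worked row: with b = 0.40, placebo is 1 - 0.60 × 0.40 = 0.76 and nemolizumab is 1 - 0.60 × 0.85 = 0.49.

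If only a fraction f of relapses is filed in each arm, the excess is f(1 - b)(r placebo - r nemolizumab). In the worked row with f = 0.5 it is 0.5 × 27 = 13.5 points. With f = 0 it is zero.

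In subjects, about 40 randomized 1:1 (Protocol 7.1) gives about 20 per arm. Relapse of 20%, 40% or 60% on placebo is then 4, 8 or 12 subjects with a PN event, and each subject is worth 5 points. SAP 4.1 gives about 100 subjects where SAP 4.3 gives 40. The percentages in the table do not depend on that number.

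**AE discontinuation**

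This line moves only if the relapse is filed as an AE and study drug is recorded as stopped because of it. If that happened for every relapse, with an assumed 5% background and relapse of 60% / 15%, placebo would be 1 - 0.95 × 0.40 = 62% and nemolizumab 1 - 0.95 × 0.85 = 19%.

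**The case against.** The strongest reply is that there is no true contradiction. The AE definition lists exacerbation of pre-existing conditions and worsening of the indication as separate items, and only the second carries the efficacy exception. The chronic-disease note fits the first item, and a specific rule ordinarily governs a general one. SAP 13.5 shows the same intent, and Protocol 14 says the SAP prevails where the two differ. Protocol 12.3 also requires a clinically significant change, so a relapse is not an automatic AE.

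Much of this stands. A reader might infer that the protocol states in two other places that PN worsening is an AE. It does not: neither place names PN, the indication or relapse. The conflict lies in general rules that lack an exception. But the preferred reading has to be worked out, and the protocol does not give it. The SAP's precedence concerns analysis and does not instruct sites, who record AEs under the protocol.

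A reader might also infer that every relapse becomes an AE leading to discontinuation. Protocol 8.3 points the other way, since treatment failure is its own reason. That entry does not forbid an AE record as well, so the route is open but not automatic.

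Finally, the AE tables are by preferred term. PN terms would appear on their own lines, the incidence of other terms would not change, and PN worsening is not an AE of special interest. No between-arm test of AEs is planned. The exposure is therefore in the aggregate lines, where a reader looks first.

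**Conclusion.** The point holds as an ambiguity that should be closed. It does not hold as a demonstrated distortion of the safety results. Read literally, two protocol rules would make a recorded relapse an AE, one sentence implies that it is not, and the SAP has no rule that handles the result. The effect runs mainly against placebo.

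Under the assumed rates, the spurious TEAE difference is at most about 7.5 to 35 points with every relapse filed, less with partial filing, and none if all sites apply the carve-out. These are ceilings that rest on assumed background and relapse rates, independence of the two, and full reporting. The 62% against 19% for AE discontinuation needs the further step of attributing every exit to an AE, and should not be read as a forecast. Nor do the documents support saying that relapses will swamp the placebo AE counts, because that depends on relapse rates and site behaviour that they do not give.

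**What to change.** 1. **Protocol 12.7.1, Protocol 12.3 and SAP 13.5:** reconcile them with one explicit statement on whether PN worsening already captured by IGA or PP NRS, including protocol-defined relapse, is reported as an AE. Cross-refer to it from the chronic-disease note and from the skin item of the examination, so that the two documents describe that item alike.
2. **SAP 13.1:** before unblinding, prespecify a list of PN-worsening preferred terms. Present the overall TEAE, severe-TEAE, exposure-adjusted and AE-discontinuation summaries with and without those terms.

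The cost is a protocol clarification, one term list and a few extra tables from existing data. No new data are needed. The second step helps even if some sites have already reported unevenly, because the summaries without PN terms do not depend on whether a site filed the relapse under a listed term.
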